6.2 Evaluation of Safety

Analyses will be performed for all patients having received ⁶⁸Ga-PSMA. The study will use the [CTCAE v4.0](#) for reporting of adverse events.

6.3 Definitions of Adverse Events

6.3.1 Adverse Event

An adverse event (also known as an adverse experience) is defined as any untoward medical occurrence associated with the use of a drug in humans, whether or not considered drug related. More specifically, an adverse event (can be any unfavorable and unintended sign (e.g., an abnormal laboratory finding), symptom, or disease temporally associated with the use of a drug, without any judgment about causality. An adverse event can arise from any use of the drug (e.g., off-label use, use in combination with another drug) and from any route of administration, formulation, or dose, including an overdose.

6.3.2 Adverse reaction

An adverse reaction is defined as any adverse event caused by the use of a drug. Adverse reactions are a subset of all suspected adverse reactions for which there is reason to conclude that the drug caused the event.

6.3.2.1 Suspected

A suspected adverse reaction is defined as any adverse event for which there is a reasonable possibility that the drug caused the adverse event. For the purposes of IND safety reporting, “reasonable possibility” indicates that there is evidence to suggest a causal relationship between the drug and the adverse event. A suspected adverse reaction implies a lesser degree of certainty about causality than an adverse reaction.

6.3.2.2 Unexpected

An adverse event or suspected adverse reaction is considered *unexpected* if it is not listed in the investigator brochure or package insert(s), or is not listed at the specificity or severity that has been observed, or, if an investigator brochure is not required or available, is not consistent with the risk information described in the general investigational plan or elsewhere in the current application.

“Unexpected,” as used in this definition, also refers to adverse events or suspected adverse reactions that are mentioned in the investigator brochure as occurring with a class of drugs or as anticipated from the pharmacological properties of the drug, but are not specifically mentioned as occurring with the particular drug under investigation.

Adverse events that would be anticipated to occur as part of the disease process are considered *unexpected* for the purposes of reporting because they would not be listed in the investigator brochure. For example, a certain number of non-acute deaths in a cancer trial

would be anticipated as an outcome of the underlying disease, but such deaths would generally not be listed as a suspected adverse reaction in the investigator brochure.

Some adverse events are listed in the Investigator Brochure as occurring with the same class of drugs, or as anticipated from the pharmacological properties of the drug, even though they have not been observed with the drug under investigation. Such events would be considered *unexpected* until they have been observed with the drug under investigation. For example, although angioedema is anticipated to occur in some patients exposed to drugs in the ACE inhibitor class and angioedema would be described in the investigator brochure as a class effect, the first case of angioedema observed with the drug under investigation should be considered *unexpected* for reporting purposes.

6.3.2.3 Serious

An adverse event or suspected adverse reaction is considered *serious* if, in the view of either the investigator or sponsor, it results in any of the following outcomes:

- Death
- Life-threatening adverse event
- Inpatient hospitalization or prolongation of existing hospitalization
- A persistent or significant incapacity or substantial disruption of the ability to conduct normal life function
- Congenital anomaly/birth defect

Important medical events that may not result in death, are life-threatening, or require hospitalization may be considered serious when, based upon appropriate medical judgment, they may jeopardize the patient or subject and may require medical or surgical intervention to prevent one of the outcomes listed in this definition. Examples of such medical events include allergic bronchospasm requiring intensive treatment in an emergency room or at home, blood dyscrasias or convulsions that do not result in inpatient hospitalization, or the development of drug dependency or drug abuse.

6.3.2.4 Life-threatening

An adverse event or suspected adverse reaction is considered *life-threatening* if, in the view of either the investigator or sponsor, its occurrence places the patient or subject at immediate risk of death. It does not include an adverse event or suspected adverse reaction that, had it occurred in a more severe form, might have caused death.

6.4 Recording of an Adverse Event

All grade 3 and above adverse events will be entered into OnCore®, whether or not the event is believed to be associated with use of the study drug. Data about these events and their severity will be recorded using the NCI CTCAE v4.0.

The Investigator will assign attribution of the possible association of the event with use of the investigational drug, and this information will be entered into OnCore® using the classification system listed below:

Relationship	Attribution	Description
Unrelated to investigational drug/intervention	Unrelated	The AE is clearly NOT related to the intervention
	Unlikely	The AE is doubtfully related to the intervention
Related to investigational drug/intervention	Possible	The AE may be related to the intervention
	Probable	The AE is likely related to the intervention
	Definite	The AE is clearly related to the intervention

Signs or symptoms reported as adverse events will be graded and recorded by the Investigator according to the CTCAE. When specific adverse events are not listed in the CTCAE they will be graded by the Investigator as *none, mild, moderate* or *severe* according to the following grades and definitions:

- Grade 0 No AE (or within normal limits)
- Grade 1 Mild; asymptomatic or mild symptoms; clinical or diagnostic observations only; intervention not indicated
- Grade 2 Moderate; minimal, local, or noninvasive intervention (e.g., packing, cautery) indicated; limiting age-appropriate instrumental activities of daily living (ADL)
- Grade 3: Severe or medically significant but not immediately life-threatening; hospitalization or prolongation of hospitalization indicated; disabling; limiting self-care ADL
- Grade 4: Life-threatening consequences; urgent intervention indicated
- Grade 5: Death related to AE

6.5 Follow-up of Adverse Events

All adverse events will be followed with appropriate medical management until resolved. Patients removed from study for unacceptable adverse events will be followed until resolution or stabilization of the adverse event. For selected adverse events for which administration of the investigational drug was stopped, a re-challenge of the subject with the investigational drug may be conducted if considered both safe and ethical by the Investigator.

6.6 Expedited Reporting

Reporting to the Data and Safety Monitoring Committee

If a death occurs during the treatment phase of the study or within 30 days after the last administration of the study drug(s) and it is determined to be related either to the study drug(s) or to a study procedure, the Investigator or his/her designee must notify the DSMC Chair (or qualified alternate) within 1 business day of knowledge of the event. The contact may be by phone or e-mail.

Reporting to UCSF Committee on Human Research (Institutional Review Board)

The Principal Investigator must report events meeting the UCSF IRB definition of "Unanticipated Problem" (UP) within 10 business days of his/her awareness of the event.

6.7 Image Processing and Analysis

A trained nuclear medicine physician blinded to results of tissue analysis will evaluate the reconstructed PET, MRI, and fused PET/MR images using a PET volume computer-assisted reading software package. A positive lesion on gallium PSMA-11 PET will be defined as a focus of activity with at least 1.5 times higher SUV compared with mediastinal blood pool that is not attributable to other etiologies of tracer distribution (e.g. excretion) or above liver background. A volume of interest (VOI) will be semiautomatically placed around each lesion, and the calculated maximum standard uptake value (SUV_{max}) will be recorded for each lesion. Adjusted SUV_{max} data will then be averaged across all lesions within a given patient ($SUV_{max-avg}$) if needed. In order to avoid clustering effects, analysis will be limited to the five largest lesions per study.

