6.8 Determination of Sample Size and Accrual Rate

Although this is a feasibility study, we will provide a sample size estimate based on the difference in sensitivities between ^{68}Ga -PSMA PET and either ^{131}I and ^{18}F -FDG. To provide an estimate of the needed sample size we assumed that half of the patients will be imaged with ^{131}I and half the patients will be imaged using ^{18}F -FDG PET within 360 days of the ^{68}Ga -PSMA-11 imaging study. We will compare the sensitivity of both ^{131}I and ^{18}F -FDG to ^{68}Ga -PSMA PET. Assuming that both ^{131}I and ^{18}F -FDG have a sensitivity of 0.65 and ^{68}Ga -PSMA PET has a sensitivity of 0.90. Our null hypothesis is that there is no difference between either ^{131}I and ^{18}F -FDG and ^{68}Ga -PSMA PET misclassification rates (H_{null} : ^{131}I / ^{18}F -FDG_misclass = PSMA PET misclass = 65%). The alternative hypothesis is that the FET PET misclassification rate is lower (H_{alt} : PSMA PET misclass < ^{131}I / ^{18}F -FDG_misclass = 65%). Given a power of 0.87, a significance level of 0.05, and a one-sided test, we will require 20 patients for comparison to ^{18}F -FDG and 20 patients for comparison to ^{131}I . This will result in a total sample size of 40. The anticipated accrual rate is approximately 1 to 2 patients per month, leading to an estimated total accrual period of up to 18 to 24 months.

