6.10 Analyses Plans

The number of ^{68}Ga PSMA-11 PET-positive lesions and number of overall thyroid cancer lesions detected by standard staging scans will be descriptively reported for each patient and correlated with the lesions observed in standard MRI imaging. In addition, the mean, range, and standard deviation of SUV_{max} (across all visualized lesions per patient) and $SUV_{max-avg}$ (across all patients in the study cohort) will be descriptively reported.

For each lesion detected on ^{18}F -FDG PET or radioiodine scintigraphy (^{131}I), the presence or absence of ^{68}Ga -PSMA-11 uptake will be reviewed and tabulated. Presence on either ^{131}I and ^{18}F -FDG will be considered true positive disease. If additional lesions are detected on ^{68}Ga -PSMA-11 as compared to ^{18}F -FDG or ^{131}I , the lesions will be characterized as either true or false positives in comparison to the appearance of the lesion on conventional imaging (thyroid ultrasound, CT and MRI). The gold standard for an individual lesion will be FDG or ^{131}I , if the individual lesion is positive on either imaging study. If the lesions are not seen on either FDG or ^{131}I , then consensus reading of conventional imaging will be performed to determine true and

false positive lesions. The total number of lesions detected using each technique will be compared, and this data will be used to determine the sensitivity and specificity of ^{68}Ga -PSMA-11 for the detection of disease. If a larger number of lesions are detected using ^{68}Ga -PSMA-11 compared to ^{18}F -FDG PET and ^{131}I , this provides promising preliminary data, which can be used to justify study in a larger clinical trial.

The patient cohort will be dichotomized by thyroglobulin level. The mean $\text{SUV}_{\text{max-avg}}$ between dichotomized subgroups will be compared using the non-parametric Mann-Whitney U test. The correlation between SUV_{max} on ^{68}Ga -PSMA PET and thyroglobulin level as a continuous variable will also be determined using Pearson correlation method.

In those patients with adequate archival FFPE the correlation between SUV_{max} on ^{68}Ga -PSMA PET and tumor PSMA expression will be explored using Pearson correlation method.

7 Study Management

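### The PSMA reader is blinded only to tissue results, and the PSMA lesion list need not be fixed before it is matched to FDG or radioiodine

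*Combined protocol and SAP*

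**What the plan says.** **Blinding.** Section 6.7 states: "A trained nuclear medicine physician blinded to results of tissue analysis will evaluate the reconstructed PET, MRI, and fused PET/MR images". No other section blinds an image reader. The review within two working days (5.1.2.1) and the per-patient acquisition review (6.9) mention no masking.

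**Positivity.** Section 6.7 calls a focus positive if it has "at least 1.5 times higher SUV compared with mediastinal blood pool that is not attributable to other etiologies" of tracer distribution, with a further reference to liver background. Volumes of interest are placed semiautomatically, and analysis is limited to the five largest lesions per study.

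**Scoring.** Section 6.10 starts from each lesion found on FDG or radioiodine and says that the presence or absence of PSMA "uptake will be reviewed and tabulated". FDG or radioiodine is the gold standard "if the individual lesion is positive on either imaging study. If the lesions are not seen on either FDG or" radioiodine, a consensus reading of conventional imaging decides. PSMA-only lesions are thus called true or false positives "in comparison to the appearance of the lesion on conventional imaging (thyroid ultrasound, CT and MRI").

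**Who may know the comparator.** Uptake on FDG, I-123 or I-131 within 360 days is an inclusion criterion (3.3.1). Staging and PSMA scans may fall on the same day, with eligibility assessed by the Principal Investigator before the scan is complete (5.1.1). No section says the PSMA reader is someone who has not seen the comparator scan.

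**Use of the result.** Comparing sensitivity and specificity is a secondary objective (2.2). Section 6.8 bases the sample size on the sensitivity difference, and 6.10 says of a higher PSMA lesion count that "this provides promising preliminary data, which can be used to justify study in a larger clinical trial".

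**The concern.** The blinding rule covers information that does not score the PSMA read and omits the information that does. Tissue enters only the exploratory correlation with PSMA expression (2.3 and the end of 6.10). FDG, radioiodine and conventional imaging decide whether a PSMA call is right.

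A reader who knows where the comparator was positive may look harder there and accept a borderline focus. A reader who knows a site was comparator-negative may be readier to put uptake there down to something other than tumour. The first behaviour raises apparent PSMA sensitivity. The second lowers the number of PSMA-only calls, and so affects both the lesion count and the classification of false positives. The lesion-by-lesion review in 6.10 invites a comparator-guided second look unless the PSMA list already exists.

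At stake is the secondary accuracy comparison and its use as grounds for a larger trial. Patient care is not at stake, because 5.1.2.1 says PSMA results will not be used for it.

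**Working it through.** **1. The plan's own figure.** Section 6.8 assumes comparator sensitivity 0.65, says "PSMA PET has a sensitivity of 0.90", and gives power 0.87 with 20 patients per comparator, one-sided alpha 0.05. An exact one-sample binomial test against a fixed 0.65 reproduces this. With success at 17 or more of 20, P(X ≥ 17 | 0.65) = 0.044 and P(X ≥ 17 | 0.90) = 0.867. The documents do not state the 17-of-20 cut-off; it is the one implied by these inputs. The change proposed below does not alter the sample size.

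**2. What is masked against what scores the read.**

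| Information | Reader masked? (6.7) | Role in accuracy scoring (6.10) |
|---|---|---|
| Tissue results | Yes | None |
| FDG, radioiodine | Not stated | Gold standard where positive |
| Ultrasound, CT, other MRI | Not stated | Decide PSMA-only lesions by consensus |
| Study MRI | No, the reader evaluates it | MRI is listed as conventional imaging |

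**3. What the threshold leaves open.** The 1.5-fold rule and the semiautomatic volumes constrain measurement. Three steps remain judgements: which foci to measure, whether uptake has another explanation, and which PSMA focus matches which comparator lesion.

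**4. Illustration of size.** Assumptions: the plan's 0.65 and 0.90 apply per lesion (6.8 counts patients); each patient has one comparator, in line with 6.8, where "we assumed that half of the patients will be imaged with" radioiodine and half with FDG; the five-lesion cap is ignored; comparator-negative lesions enter the reference only as PSMA-only lesions confirmed by consensus. The rates of 10% and 25% are assumed and have no source in the documents.

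Per 100 reference-positive lesions, 65 are comparator-positive and 35 are PSMA-only. PSMA misses M = 10 of the 65, so PSMA sensitivity is (65 − 10 + 35)/100 = 0.90. Let u be the share of misses upgraded and d the share of PSMA-only calls dropped, which then leave the reference:

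- PSMA sensitivity = (65 − M + uM + 35(1 − d)) / (100 − 35d)
- Comparator sensitivity = 65 / (100 − 35d)

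| Scenario | PSMA | Comparator | Gap |
|---|---|---|---|
| No influence | 0.90 | 0.65 | 0.25 |
| u = 10% | 0.91 | 0.65 | 0.26 |
| u = 25% | 0.925 | 0.65 | 0.275 |
| d = 10% | 86.5/96.5 = 0.896 | 65/96.5 = 0.674 | 0.22 |
| d = 25% | 81.25/91.25 = 0.890 | 65/91.25 = 0.712 | 0.18 |

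If both behaviours occur, the gap is 0.233 at 10% each and 0.205 at 25% each. If dropped lesions stay in the reference as PSMA misses, the gap is 0.215 (d = 10%) or 0.163 (d = 25%).

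**5. Direction.** If both tests truly had sensitivity 0.65 (M = 35), the gap would move from 0 to +0.035 or +0.088 under upgrades, and to −0.036 or −0.096 under drops. The sign depends on which behaviour dominates, and the documents do not say.

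**The case against.** The strongest reply is that the plan is silent; it does not prescribe an unblinded read. No section gives the reader the comparator scans, and the site may already read PSMA first. The threshold and semiautomatic volumes limit discretion. This is a single-centre pilot whose primary objective is feasibility and utility, and 6.10 claims only preliminary data. At the plan's values, upgrades move the gap by just 0.010 to 0.025, while the standard error of a sensitivity of 0.90 in 20 patients is √(0.90 × 0.10/20) = 0.067.

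Much of this stands. It sets the weight of the point and rules out stronger readings:

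- A reader might infer that the comparison cannot separate tracer performance from reader knowledge at all. The text does not support that, since it does not establish an unblinded read and the threshold removes part of the discretion.
- A reader might infer that PSMA sensitivity will be overstated. Step 5 shows the shift can go either way.
- A reader might treat 35 in 100 as a ceiling on the lesions that consensus decides. It only follows from the assumed 0.65, would be larger at a lower comparator sensitivity, and leaves out the false positives that consensus also decides.

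What the reply does not remove is the omission. Systematic influence on reads does not average out as sampling error does, and masking cannot be restored once reads have been made with the comparator in view.

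**Conclusion.** The point holds as a gap in the plan. The one blinding rule leaves out every source used to score PSMA calls, and 6.10 allows matching before the PSMA list is fixed. The secondary sensitivity and specificity comparison may therefore not fully separate tracer performance from reader knowledge.

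Direction and size are unknown. The shifts from 0.25 to 0.26 or 0.275, or to 0.22 or 0.18, rest on assumed influence rates applied per lesion, with one comparator per patient and no five-lesion cap. They do not address specificity. The primary objective, patient care and the sample size are unaffected. This is a cheap improvement that should be made before further reads; it is not a reason to hold the study.

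**What to change.** **In 6.7:** require the PSMA reader to record and lock the lesion list (site, positive or negative, SUVmax) before seeing FDG, radioiodine, ultrasound, CT or separately acquired MRI images or reports. Choose any five largest PSMA lesions from the locked list. Record whether the reader had already seen that patient's comparator scan.

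**In 6.10:** match to the comparator only after the lock, and report any later change separately.

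**Order of reads:** if the same physician does both, the locked read comes before the two-working-day review (5.1.2.1) and the acquisition review (6.9). The timing of those reviews does not change, and they can stay unblinded.

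**Limits to state in the plan:**

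- The study MRI is part of the index test and also counts as conventional imaging, so masking to it is not possible.
- Eligibility tells every reader that at least one comparator-positive site exists. Masking hides location, number and which sites are negative.
- Sites go to consensus because PSMA was positive there, so withholding the PSMA images from the consensus readers gives only limited protection.

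**Cost:** wording in two sections and two form fields (lock date; comparator already seen, yes or no). There is a real scheduling constraint when one physician does both reads, and localisation is slightly harder without prior scans. No extra reader, scan or patient is needed.

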5.1.2 Study Period

5.1.2.1 ^{68}Ga -PSMA PET/MRI

Subjects will be injected with ^{68}Ga -PSMA [REDACTED] and, if needed, transported to the imaging site. After the biodistribution period (50 to 80 minutes after radiotracer injection), coverage for the scan will extend from the patient's vertex through the thighs.

A standard neck MRI will be performed concurrently with the PET/MRI. This MRI will be performed without and with gadolinium contrast intravenously. Gadolinium contrast will not be administered if the patient cannot receive contrast based on Radiology Department guidelines. A whole body (vertex to toes) MRI (PET/MRI) will be performed for attenuation correction and anatomic localization. Patients may be given lorazepam as needed, to keep them from feeling anxious during the scan. The entire imaging study will take roughly 60 minutes. Imaging will be performed at [REDACTED] UCSF [REDACTED].

No formal report of the findings from imaging studies will be created. Each study will be reviewed by a board-certified nuclear medicine physician and a board-certified radiologist within two working days of the completion of the study. ^{68}Ga -PSMA PET results will not be used for clinical care. If any unexpected findings are visualized, these will be reported to the treating health care provider, who will then contact the patient if additional work-up needs to be performed.

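### The MRI from the PSMA session may also serve as reference for PSMA-only lesions, in a consensus read with no stated masking to PSMA, so false positives may be under-counted

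*Combined protocol and SAP*

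**What the plan says.** Section 6.7 assigns the PSMA read to "A trained nuclear medicine physician blinded to results of tissue analysis", who "will evaluate the reconstructed PET, MRI, and fused PET/MR images using a PET volume computer-assisted reading software package". Tissue results are the only thing this reader is said to be masked to. A positive lesion needs uptake of at least 1.5 times mediastinal blood pool, with a further reference to liver background. It also needs a judgement that the focus is "not attributable to other etiologies of tracer distribution (e.g. excretion").

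Section 5.1.2.1 describes two MRI acquisitions in the PSMA session: "A standard neck MRI will be performed concurrently with the PET/MRI", and "A whole body (vertex to toes) MRI (PET/MRI) will be performed for attenuation correction and anatomic localization".

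Section 6.10 treats any lesion positive on FDG or radioiodine as true disease. Additional PSMA lesions are classed as true or false positives "in comparison to the appearance of the lesion on conventional imaging (thyroid ultrasound, CT and MRI"). Where neither FDG nor radioiodine shows the lesion, "then consensus reading of conventional imaging will be performed to determine true and" false positive lesions. Section 6.10 also says that lesion counts will be "correlated with the lesions observed in standard MRI imaging". It does not say which MRI is meant, who the consensus readers are, or what they may see.

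**The concern.** An index test should not help to verify itself. Here one MRI can inform the call that a focus is PSMA-positive, and the same MRI can then help decide whether that call was right. This is incorporation bias. The second risk is review bias: the consensus step exists for lesions that PSMA found and the comparators did not, so readers would ordinarily know the site was PSMA-positive unless the plan hid it from them.

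The step carries weight. It is the only place where 6.10 can generate a PSMA false positive. In a patient with one comparator scan it is also the main route by which that comparator can be shown to have missed disease. Comparing sensitivity and specificity is a secondary objective (2.2), and 6.10 treats a higher PSMA lesion count as support for a larger trial.

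**Working it through.** **1. The plan's own figure.** No figure in the documents bears directly on this point. The nearest is the power of 0.87 in 6.8. An exact one-sample binomial test with n = 20, rejecting at 17 or more, gives P(X ≥ 17 | 0.65) = 0.044 and P(X ≥ 17 | 0.90) = 0.867, which reproduces it. That calculation uses no adjudicated lesions, so the sample size is unaffected.

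**2. Following one MRI through the plan.**
- *Index side (6.7):* the reader has PET, MRI and fused images together. The uptake threshold is numeric, but ruling out other causes of tracer activity is a judgement that anatomy can inform.
- *Availability (3.3.1, 5.1, 5.1.1, 5.1.2.1 and the schedule table in 5.1.4):* entry requires FDG PET/CT or radioiodine scintigraphy, not a separate MRI or ultrasound. Other standard scans are done only when clinical care calls for them, and staging scans may be up to 360 days old. The session MRI is the only MRI scheduled for every patient. For a patient with no other MRI, it is the only one that 6.10 can mean.
- *Reference side (6.10):* MRI is one of three permitted modalities, and the session MRI is not excluded. Sections 5.1.2.1 and 6.10 both call an MRI standard, which does not separate them.
- *Masking:* none to PSMA is stated for the consensus read.

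**3. What the step decides.** Let C be comparator-positive lesions (all true by rule) and A the PSMA-only lesions accepted as true. In patients with one comparator, as 6.8 assumes, comparator sensitivity is C/(C + A). To reach 0.65 at lesion level, 65 comparator-positive lesions need A = 35, since 65/(65 + 35) = 0.65. The contrast therefore depends heavily on A.

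**4. Illustration.** All inputs here are assumptions: 20 PSMA-only lesions, 10 real and 10 not; 100 comparator-positive lesions, 80 of them PSMA-positive. Let q be the share of unreal lesions wrongly accepted and s the share of real ones confirmed. Take q = 0.10 for a masked read and 0.30 to 0.50 for an unmasked read on the same MRI.

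Counted false positives = 10(1 − q) + 10(1 − s); A = 20 minus that count; comparator sensitivity = 100/(100 + A); PSMA sensitivity = (80 + A)/(100 + A).

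| q | s | False positives | A | Comparator | PSMA |
|---|---|---|---|---|---|
| truth | – | 10 | 10 | 0.909 | 0.818 |
| 0.10 | 1.0 | 9 | 11 | 0.901 | 0.820 |
| 0.30 | 1.0 | 7 | 13 | 0.885 | 0.823 |
| 0.50 | 1.0 | 5 | 15 | 0.870 | 0.826 |
| 0.10 | 0.8 | 11 | 9 | 0.917 | 0.817 |
| 0.30 | 0.8 | 9 | 11 | 0.901 | 0.820 |
| 0.50 | 0.8 | 7 | 13 | 0.885 | 0.823 |

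Against the masked read, counted false positives fall by (9 − 7)/9 = 22% to (9 − 5)/9 = 44% when s = 1.0, and by (11 − 9)/11 = 18% to (11 − 7)/11 = 36% when s = 0.8. The comparator-minus-PSMA gap, (20 − A)/(100 + A), moves from 9/111 = 0.081 to 7/113 = 0.062 and 5/115 = 0.043 when s = 1.0. When s = 0.8 it moves from 11/109 = 0.101 to 0.081 and 0.062. Both shifts favour PSMA.

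**5. Against the truth the sign is not fixed.** With s = 0.8 the masked read over-counts by one (11 against 10), and the unmasked read at q = 0.30 under-counts by one (9 against 10). Unmasking may also raise s. Going from q = 0.10, s = 0.8 to q = 0.30, s = 1.0 takes the count from 11 to 7, and 2 of those 4 reclassifications are correct.

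**The case against.** The best reply is that the plan is silent rather than wrong. It never says that the session MRI will be the reference or that the consensus readers will see the PSMA PET, and ultrasound and CT may contribute. That stands: both practices are permitted, not stated. It does not remove the point, because nothing rules them out and the trigger for the read discloses PSMA positivity.

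Some stronger readings are tempting but not supported:
- *PSMA is credited with what gadolinium MRI found.* Positivity requires a tracer focus above threshold, so an MRI abnormality without uptake cannot become a PSMA lesion. The dedicated diagnostic MRI covers only the neck, and contrast is omitted where departmental guidelines preclude it.
- *Confirmation would approach 100% whatever the truth.* That would need a rule that only foci with an MRI correlate are called. Section 6.7 has no such rule.
- *The PSMA PET must be read before the neck MRI is opened.* For an integrated PET/MRI test this is a debatable trade-off, and the point does not need it.

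It is also fair that the primary objective is feasibility and utility, that PSMA results do not guide care (5.1.2.1), and that 6.10 defines no lesion-level true negatives. The last is a separate gap, and it means that the effect on specificity cannot be calculated here. These limit the importance of the point, but the sensitivity comparison remains a stated objective.

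**Conclusion.** The concern holds as a risk built into the reference standard. The same-session MRI forms part of the PSMA read and is eligible to verify PSMA-only lesions, in a read triggered by PSMA positivity with no stated masking. Relative to a masked, independent reference, false positives may be under-counted and the sensitivity comparison may tilt toward PSMA.

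The documents give no figure to size this. The 18–44% reduction and the narrowing of the sensitivity gap by about 0.02 to 0.04 rest entirely on the assumed lesion counts and acceptance rates above. A reader might infer that false positives are under-counted in fact. The documents do not support that, because real lesions not visible on conventional imaging would be recorded as false positives and the net error could go either way. The stated power is untouched.

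**What to change.** Change 6.10 as follows.
- Have the planned consensus readers record suspicious lesions on conventional imaging before they see the PSMA PET, and only then match that list to the PSMA-only lesions. Say who these readers are, since the plan does not.
- Flag each PSMA-only lesion whose only support is the same-session MRI.
- Report the true/false split, sensitivity and specificity with and without the flagged lesions.

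The session MRI stays available to the PSMA reader, and no new scans or patients are needed. The cost is some extra reading time, because a full listing takes longer than looking at PSMA-identified sites. The downside is that subtle real lesions missed on the masked list may be recorded as false positives, which is why both sets of results should be shown.
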